### 13.3 Analysis Plan

#### 13.3.1 Primary Endpoint

The primary endpoint is delayed recall, as determined by the relative change in HVLT-R delayed recall score from the start of treatment to 3 months after the start of treatment. To test the null hypothesis H0, the primary endpoint will be analyzed using the one-sided one sample t-Test with a significance level of 0.05.

#### 13.3.2 Secondary Endpoints

##### 13.3.2.1 Cognitive Function and Fatigue

All the secondary cognitive and fatigue endpoints will be analyzed similar to the primary endpoint. Additionally, the relationship between the change from baseline through 12 months in cognitive and fatigue endpoints will be evaluated using Spearman correlation coefficients.

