#### 11.3.1 Summary of Required Fatigue Evaluations For All Patients

##### 11.3.1.1 Multidimensional Fatigue Inventory (MFI-20)

The MFI-20 is a multidimensional, self-report instrument designed to measure fatigue. It covers the following dimensions: General Fatigue, Physical Fatigue, Mental Fatigue, Reduced Motivation and Reduced Activity. A subscore from 4 to 20 is reported for each dimension, with 20 corresponding to maximal fatigue.

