### 13.2 Sample Size

The primary endpoint will be delayed recall, as measured by the relative (percent) change in HVLTR delayed recall score from the start of treatment to 3 months after the start of treatment.

The sample size calculation will address the specific primary hypothesis that WBRT-HA/SIB reduces decline in delayed recall (from baseline to 3 months). We do not expect improvement in delayed recall; at best, we anticipate a preservation of delayed recall. Data from a randomized trial showed that the decline in HVLTR delayed recall score was 64% at 4 months for those getting whole brain radiation for brain metastases (Chang et al., 2009). We anticipate that WBRT-HA/SIB will have better delayed recall functioning at 3 months than WBRT alone. Detecting a 30% average relative loss due to WBRT-HA/SIB suggests a 50% relative improvement over previous results. The null and alternative hypotheses are:

$$H_0: \Delta HVLTR = 0.60 \text{ vs. } H_A: \Delta HVLTR \leq 0.30$$

$\Delta$ HVLT-R is the mean of relative decline between baseline and 3 month after treatment in this patient population. For patient individual i, the relative decline is calculated as follows:  $\Delta$ HVLT-Ri = ( HVLT-Ri0 - HVLT-Ri3 ) / HVLT-Ri0 , where HVLT-Ri0 and HVLT-Ri3 denote individual patient scores at baseline and 3 months after treatment, respectively.

Initial sample size calculation:

Based on the one-sided one sample t-test, assuming a standard deviation of 41%, with alpha=0.05 (one-sided), a total of 9 analyzable patients would ensure 80% statistical power to detect a 30% average relative loss in delayed recall at 3 months. Assuming a death rate of 60% prior to 3 months and a 10% in-evaluable rate, the target sample size will be 34 registered patients.

Sample size re-estimation based on internal pilot study:

The internal pilot consists of 32 patients enrolled at baseline, among which 9 patients have complete information on HVLT-R delayed recall score at the start of treatment and 3 months after the start of treatment. For the 9 patients, the mean and standard error of relative (percent) change (decline) in HVLT-R delayed recall score is 31% and 51%. We re-estimate the required sample size using the updated standard error.

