Based on the one-sided one sample t-test, assuming a standard deviation of 51%, with alpha=0.05 (one-sided), a total of 18 analyzable patients would ensure 80% statistical power to detect a 30% average relative loss in delayed recall at 3 months. Assuming a death rate of 60% prior to 3 months and a 10% in-evaluable rate, the target sample size will be 50 registered patients. Therefore, additional 18 patients need to be recruited at the second stage.

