##### 13.3.2.2 MFI

Change in MFI domain scores from baseline to each post-baseline assessment point will be analyzed using mixed models for repeated measures.

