## Appendix III:

### Neurocognitive Function Assessments Background Information and Test Instructions

There are three immediate recall responses, one delayed recall response, and one delayed recognition response in the HVLTR. The response is the number of words the patient can recall out of 12 words for recall responses and the difference of the listed words correctly and incorrectly recalled for recognition response. The response from Trail Making Test, parts A & B is the time takes to finish each test less than 3 and 5 minutes, respectively. There are three responses for the COWAT, and each response is the number of words starting with a provided letter of the alphabet that the patient can produce in one minute.

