**Part C – Delayed Recognition**

**Examiner:** *“Now I’m going to read a longer list of words to you. Some of them are words from the original list, and some are not. After I read each word, I’d like you to say “Yes” if it was on the original list or “No” if it was not. Was [word] on the list?”*

- Check either the “Y” (Yes) or “N” (No) box next to each word to indicate the patient’s response.
- Guessing is allowed.
- If the test is discontinued or omitted, please mark this on the bottom of the test form and indicate the reason on the Tests Discontinued/Not Done CRF.

The score for this portion of the HVLТ-R is the number of list words (i.e., words that in CAPS) correctly identified (“yes” response) minus the number of non-list words (i.e., words in lower case) incorrectly identified (“yes” response). Therefore, the actual score can range from –12 (*no list words identified and all non-list words identified*) to +12 (*all list words identified and no non-list words identified*).

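### The secondary cognitive and fatigue endpoints inherit the primary ratio test, which as written reverses direction for Trail Making (and possibly MFI-20), fails at zero or negative baselines, and has no stated null

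*Combined protocol and SAP*

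**What the plan says.** Section 13.3.2.1 gives one rule for the whole secondary battery: "All the secondary cognitive and fatigue endpoints will be analyzed similar to the primary endpoint". The endpoints listed in section 13.1.2 are HVLT-R free recall and delayed recognition, COWAT, Trail Making A and B, MOS, MMSE and MFI-20. No direction, null or margin is attached to any of them.

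The method they are sent to is set out in full. Section 13.2 defines a relative decline for each patient, (baseline − month 3)/baseline. The parameter "is the mean of relative decline between baseline and 3 month after treatment in this patient population", with a null of 0.60 and an alternative of 0.30 or less. Section 13.3.1 adds that "the primary endpoint will be analyzed using the one-sided one sample t-Test with a significance level of 0.05". Low values therefore count as success.

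The protocol's own scoring rules are:

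- Trail Making (Appendix III): "The response from Trail Making Test, parts A & B is the time takes to finish each test". Higher is worse.
- MFI-20 (section 11.3.1.1): "A subscore from 4 to 20 is reported for each dimension, with 20 corresponding to maximal fatigue". Higher is worse.
- HVLT-R delayed recognition (Appendix III, Part C): "Therefore, the actual score can range from" −12 to +12. Zero and negative values are possible.

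For MFI-20 there is a second instruction in section 13.3.2.2: "Change in MFI domain scores from baseline to each post-baseline assessment point will be analyzed using mixed models for repeated measures". The plan does not say whether it replaces the general rule or is added to it.

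**The concern.** The primary metric suits a score that is positive at baseline and for which higher is better. Several of the secondary scales do not meet one or both conditions. On a higher-is-worse scale, deterioration gives a negative decline, which the lower-tail test counts as favourable. On a scale that passes through zero, the ratio can be undefined or change sign. And a one-sample test cannot be run without a null, which no secondary endpoint has.

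Two things are at stake. An analyst who follows the sentence literally could report slower Trail Making as a favourable result. One who sees the problem must choose scale, direction and null test by test, possibly after seeing the data. Section 1.7 says that comparing the endpoints with historical WBRT data will inform whether a phase III trial is warranted, so these readings may carry weight.

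**Working it through.** **1. The plan's own figure.** Inputs from section 13.2: SD 0.51, difference 0.60 − 0.30 = 0.30, one-sided alpha 0.05, power 80%. By the normal approximation, n = (0.51 × 2.4865/0.30)² = 17.87, so 18. This matches the plan: "a total of 18 analyzable patients would ensure 80% statistical power". Registered patients: 18/(0.4 × 0.9) = 50, also as stated. So 18 is the analysable number used below.

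**2. Direction on higher-is-worse scales.** Formula: (baseline − follow-up)/baseline. No SD or null is needed.

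| Scale | Change | Meaning | Score |
|---|---|---|---|
| Trail Making | 60 to 75 s | worse | (60 − 75)/60 = −0.25 |
| Trail Making | 60 to 45 s | better | (60 − 45)/60 = +0.25 |
| MFI-20 subscore | 10 to 14 | worse | (10 − 14)/10 = −0.40 |
| MFI-20 subscore | 4 to 20 | worst possible | (4 − 20)/4 = −4.0 |
| MFI-20 subscore | 20 to 4 | best possible | (20 − 4)/20 = +0.80 |

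Every worsening falls on the side that the test counts as success. The MFI-20 range is also lopsided, from −4.0 to +0.80. The direction is correct for free recall, COWAT and MMSE, where higher is better. The documents do not give the MOS direction.

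**3. Zero and negative baselines.** For delayed recognition:

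- baseline 0: division by zero, undefined;
- −2 to −6 (worse): (−2 + 6)/(−2) = −2.0, scored as favourable;
- −2 to +4 (better): (−2 − 4)/(−2) = +3.0, scored as a 300% decline.

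A zero baseline also makes the ratio undefined for free-recall counts, COWAT and the primary delayed-recall count. Only recognition can go negative. The documents do not say how often such baselines occur.

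**4. The null.** The 0.60 in section 13.2 is written for delayed recall and follows a delayed-recall figure from an earlier trial. Section 1.7 names a historical WBRT source but gives no value for any secondary test.

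**5. Illustration of the consequence.** Suppose the observed mean Trail Making score is −0.25, with n = 18 and 17 df, against an assumed null of 0. Then t = −0.25/(SD/√18).

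| SD | Source | t | One-sided p, favourable tail |
|---|---|---|---|
| 0.41 | initial plan value, delayed recall | −2.59 | 0.010 |
| 0.51 | re-estimated value, delayed recall | −2.08 | 0.026 |
| 0.70 | assumed | −1.52 | 0.074 |

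No secondary SD is given, so these p-values only show what the reversal could do. Section 13.2 also calls the pilot 51% a standard error in one paragraph and uses it as an SD in the next. If the first label were literal, the SD would be 0.51 × √9 = 1.53 and p about 0.25.

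**The case against.** The strongest reply is that the sentence asks for a similar analysis, not an identical one. Objective 2.2.1 frames the battery in terms of decline, and a competent analyst would reverse the sign for a timed test. That is probably what would happen, so a reader should not infer that the trial will in fact report worsening as benefit. But the reversal is not written down, and it would neither repair recognition nor supply a null.

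Second, MFI-20 has its own section, with a mixed model on change that uses neither the ratio nor a one-sided test. This largely stands. It would be too strong to say that the fatigue analysis is wrong; the remaining fault is that the general rule also covers fatigue and neither section is given precedence.

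Third, a reader might infer that 0.60 carries over to every test, so that modest losses would pass easily. At SD 0.51 and n = 18, a true 20% loss would reject 0.60 with probability 94% (75% to 99% for SD 0.70 to 0.41). The documents do not support that reading: sections 13.2 and 13.3.1 tie the null to delayed recall. The supported statement is that no secondary null is given.

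Finally, these are secondary endpoints in a single-arm phase II trial with no decision rule attached, and raw times and subscores would show a worsening. This limits the weight of the point but does not make the stated rule usable.

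**Conclusion.** The point holds as a fault in the secondary analysis rule and should be corrected before those data are analysed. Taken as written, section 13.3.2.1 reverses direction for Trail Making, and for MFI-20 unless section 13.3.2.2 is meant to replace it. It gives undefined or sign-reversed values for recognition baselines at or below zero, and it leaves every secondary test without a null.

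The reversal follows from the protocol's formula and scoring rules alone. Its numerical effect on any test result cannot be determined from the documents, because the secondary SDs, the nulls and the frequency of problem baselines are all missing.

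A reader might conclude either that the primary test shares the whole fault or that it is untouched. Neither is right. Its direction and null are sound on this point, but its ratio is also undefined for a patient with a baseline delayed-recall score of zero.

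**What to change.** Replace the first sentence of section 13.3.2.1 with:

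> For HVLT-R free recall and delayed recognition, COWAT, TMT A and B, MMSE and, where collected, MOS (scoring direction to be stated), report the mean absolute change from baseline to 3 months with a two-sided 95% CI, signs aligned so that positive means worsening. The 0.60 null applies only to HVLT-R delayed recall. MFI-20 is analysed by the mixed model of 13.3.2.2, with the 3-month contrast reported.

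Relative change may be reported in addition for free recall, COWAT and MMSE where the baseline is above zero, which keeps a link to the primary metric. A zero baseline on the primary delayed-recall score needs its own stated rule, which this text does not supply. Nor does it supply the time-to-failure analysis named in objective 2.2.1.

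The cost is a wording change; no new data or patients are needed. Secondary results become estimates with intervals instead of one-sided tests. The 32-patient internal pilot is already enrolled, so this is a mid-trial change: it should be dated and made before the secondary data are analysed.

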##### 13.3.2.2 MFI

Change in MFI domain scores from baseline to each post-baseline assessment point will be analyzed using mixed models for repeated measures.

##### 13.3.2.3 Radiographic Progression

The Kaplan-Meier estimator will be used to determine the median time to radiographic progression for this patient population (along with 95% confidence intervals). The Cox proportional hazards regression model will be used to evaluate the effects of covariates of interest on time to radiographic progression.

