### **2.2 Secondary Objectives**

- 2.2.1 Evaluate time to neurocognitive failure as measured by cognitive decline on a battery of tests: the HVLT-R for free recall, delayed recall, and delayed recognition; the Controlled Word Association Test (COWAT); the Trail Making Test Parts A and B (TMT); the Medical Outcomes Scale-Cognitive Functioning Subscale (MOS); and the Mini-Mental Status Examination (MMSE) after WBRT-HA/SIB for brain metastases
- 2.2.2 Evaluate fatigue, as assessed by the Multidimensional Fatigue Inventory (MFI-20) after WBRT-HA/SIB for brain metastases.
- 2.2.3 Evaluate local control within the brain
  - 2.2.3.1 Evaluate local control of brain metastases treated with integrated boost
  - 2.2.3.2 Evaluate local control within the region of brain within the CTV receiving 20 Gy.
  - 2.2.3.3 Evaluate local control within the hippocampal regions.
- 2.2.4 Evaluate time to radiographic progression after WBRT-HA/SIB for brain metastasis.
- 2.2.5 Evaluate overall survival after WBRT-HA/SIB for brain metastasis.
- 2.2.6 Evaluate adverse events according to CTCAE criteria.
- 2.2.7 Evaluate health-related quality of life [as assessed by the Functional Assessment of Cancer Therapy with Brain Subscale (FACT-BR) and the Euroqol EQ-5D before and after (WBRT-HA/SIB)]

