## 3.0 PATIENT SELECTION

### 3.1 Conditions for Patient Eligibility

- 3.1.1 Pathologically (histologically or cytologically) proven diagnosis of a non-hematopoietic malignancy other than small cell lung cancer and germ cell malignancy.. Direct biopsy of CNS lesions is not necessarily required although could constitute an allowed site of tissue confirmation as medically prudent. Patients who have been disease free for more than 5 years prior to the appearance of CNS metastases should undergo repeat biopsy of either a systemic metastasis or the CNS metastases to confirm the recurrent malignancy.
- 3.1.2 Patients with measurable brain metastasis outside a 5-mm margin around either hippocampus
- 3.1.3 Patients with measurable brain metastasis who have not been or will not be treated with SRS or surgical resection (Note: These treatment options are only permitted at relapse)
- 3.1.4 History/physical examination within 28 days prior to registration
- 3.1.5 Patients must fall into RTOG recursive partitioning analysis (RPA) class I or II
- 3.1.6 Patients must have a life expectancy of at least 3 months.
- 3.1.7 Age  $\geq$  18 years
- 3.1.8 Karnofsky performance status  $\geq$  70
- 3.1.9 Patients must provide study-specific informed consent prior to study entry
- 3.1.10 Women of childbearing potential and male participants must practice adequate contraception
- 3.1.11 Women of childbearing potential must have a negative, qualitative serum pregnancy test  $\leq$  2 weeks prior to study entry
- 3.1.12 Patients who had radiosurgery  $>$  3 months prior to registration are eligible

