#### 11.6 Measurement of Response

Patients will undergo brain MRI prior to study entry (the MRI obtained for hippocampal contouring can be used for this purpose) and every 3 months until death or until 2 years after WBRT-HA/SIB, whichever comes first.

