11.6.1.2 Definition of CNS Progression

CNS progression will be defined as a defined increase (see below) in perpendicular bidimensional tumor area for any of the tracked brain metastases, or the appearance of any new brain metastasis on a follow-up MRI.

For lesions < 1cm in maximum diameter, a minimum increase of 50% of perpendicular bi-dimensional treatment area will be necessary to score as progression. This caveat is included to account for potential variability in measurement, which will be most susceptible to proportionate errors at smaller sizes.

For lesions > 1cm in maximum diameter, the definition will use a 25% rule for change.

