#### Overall Survival

The Kaplan-Meier estimator will be used to determine the median time to death for this patient population (along with 95% confidence intervals). The Cox proportional hazards model will be used to evaluate the effects of covariates of interest on survival.

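### Time to radiographic progression has no rule for death or unscanned patients, the text and the form differ on which lesions and region are recorded, and local control has no estimator

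*Combined protocol and SAP*

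**What the plan says.** **Progression.** Objective 2.2.4 reads "Evaluate time to radiographic progression after WBRT-HA/SIB for brain metastasis". Section 13.3.2.3 states: "The Kaplan-Meier estimator will be used to determine the median time to radiographic progression for this patient population". It adds a 95% interval and a Cox model with unnamed covariates. Under 11.6.1.2 an event is a sufficient increase in lesion area "for any of the tracked brain metastases, or the appearance of any new brain metastasis on a follow-up MRI". Death is not part of it and has its own analysis: "The Kaplan-Meier estimator will be used to determine the median time to death for this patient population". Under 11.6, MRI is repeated "every 3 months until death or until 2 years after WBRT-HA/SIB, whichever comes first".

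**Early death.** Section 13.2 reaches 50 registered patients as follows: "Assuming a death rate of 60% prior to 3 months and a 10% in-evaluable rate". Criterion 3.1.6 reads "Patients must have a life expectancy of at least 3 months". Of the 32 pilot patients, 13.2 says only "among which 9 patients have complete information on HVLT-R delayed recall score" at both time points, with no reasons for the rest.

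**Recording.** Section 11.6.1.1 records lesion area for the one to three largest baseline metastases. It classifies new lesions by the hippocampal avoidance region, that is, the hippocampus plus 5 mm. Appendix II has nine rows for treated metastases and asks whether new lesions are inside or outside the hippocampus, with no margin. Sections 6.1.1.2 and 6.4.3 give every metastasis its own boosted target.

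**Local control.** Objective 2.2.3 has three parts: boosted metastases, the whole-brain region treated to 20 Gy, and the hippocampal regions. Section 13.1.2 does not list local control, and 13.3 has no analysis for it.

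**The concern.** The plan does not say whether a death without progression is an event, a censored time or a competing event, nor what happens to a patient who is never rescanned. If many patients die before the first scan, as 13.2 assumes, that unstated choice largely decides the reported median. If deaths are censored, a reader may take the median as the typical registered patient's outcome, which it is not.

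The recording rules matter because disease control near the hippocampus is the main oncologic risk discussed in 1.4. Growth of a fourth or later boosted lesion, and recurrence in the 5 mm shell, are what objectives 2.2.3.1 and 2.2.3.3 need. Followed literally, 11.6.1.1 can miss the first and the form can misplace the second. Section 1.7 says the study is to inform whether a phase III trial is warranted.

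**Working it through.** **1. The planning input.** The 60% death rate is used in the sample size. Section 13.2 takes SD 0.51, difference 0.60 - 0.30 = 0.30, one-sided alpha 0.05 and 80% power. By the normal approximation, n = [(1.645 + 0.842) × 0.51/0.30]² = 17.87, so 18. Registered N = 18/(0.40 × 0.90) = 50. Both of the plan's figures reproduce. The Schema still gives 102, but the percentages below do not depend on N.

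**2. When the median is reached.** Assume deaths are censored, every survivor is scanned at the first scheduled MRI, there is no earlier scan, and all events fall at that scan. With d the proportion dead beforehand, 50(1 - d) patients are at risk and Kaplan-Meier reaches 0.5 after half of them progress.

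| d | Scanned | Progressions needed | Share of 50 registered |
|---|---|---|---|
| 20% | 40 | 20 | 40% |
| 40% | 30 | 15 | 30% |
| 60% | 20 | 10 | 20% |

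The counts change if events are spread over scans. At d = 60%, let 4 of 20 progress, then 6 die, then 4 of the remaining 10 progress. The curve is at 0.80 × 0.60 = 0.48 after 8 events.

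**3. How far the death rule moves the result.** This is an illustration with independent exponential times. The death hazard is -ln(0.40)/3 = 0.305 per month. For progression, take 50% by 6 months, borrowed from the intracranial control of about 50% that 1.4 quotes for conventional WBRT: -ln(0.50)/6 = 0.116 per month.
- Death censored: median ln 2/0.1155 = 6.0 months.
- Death an event: median ln 2/0.421 = 1.6 months.
- Death competing: cumulative incidence levels off at 0.1155/0.421 = 27%, so there is no median.

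If 30% or 70% progress by 6 months, the two medians are 11.7 and 1.9 months, or 3.5 and 1.4 months, and the plateaus are 16% and 40%. If only 20% die by 3 months (hazard 0.074; 50% progressed by 6 months), the medians are 6.0 and ln 2/0.190 = 3.6 months, and the plateau is 0.1155/0.190 = 61%.

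**4. Time origin.** Objective 2.2.4 fixes no day zero. Section 12.0 and Appendix I count from the end of radiotherapy; the primary endpoint counts from its start. Treatment lasts 2 to 2.5 weeks, so the choice moves times by about 0.5 month.

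**5. Unmeasured lesions.** With m lesions and three recorded, (m - 3)/m are not: 1/4 = 25% at m = 4 and 6/9 = 67% at m = 9. Criterion 3.2.1 allows nine, but the Schema requires fewer than nine, which gives 5/8 = 62.5%. The updated series in 1.4 averages 1133/371 = 3.05 lesions per patient (its 8.6% equals 32/371). The share of patients with more than three is not given.

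**6. Region.** In the first series in 1.4, 9 of 272 metastases (3.3%) lay within 5 mm of the hippocampi and none inside them. The form, read literally, would place all nine outside; 11.6.1.1 would place them in the avoidance region.

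**7. Local control.** Section 11.6.1.1 names three recurrence categories: brain, avoidance region, and elsewhere in the brain. None isolates boosted lesions, and no denominator or estimator is given.

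**The case against.** Several points on the other side are fair.

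- **Overstatement of progression.** At the first scan, one minus Kaplan-Meier divided by the cumulative incidence is 1/(1 - d), or 2.5 at d = 60%. A reader might infer that the plan overstates progression 2.5-fold. The documents do not support that. Section 13.3.2.3 reports a median, never a proportion, and the ratio compares two different quantities. Cumulative incidence of scan-detected progression also counts patients who die unscanned as not progressed, and some may have progressed.
- **The 60% is not data.** It is a planning assumption that sits awkwardly with the life-expectancy criterion. The 23 pilot patients without paired scores (32 - 9) cannot be read as deaths. Hence the 20% and 40% rows.
- **Earlier scans are possible.** Section 12.0 lists a progression MRI separately from the scheduled forms, so some patients may be scanned before 3 months.
- **The form has room.** Nine rows can already hold every boosted lesion, and its region item may be shorthand for the avoidance region. Lost data are not shown; conflicting instructions are.
- **The 0-of-9 split.** One might infer that the form would miss most avoidance-region recurrences. Section 1.4 assumes only that risk in the region as a whole scales as at presentation; it says nothing about the split within the region after treatment.

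Treating death as censored is a familiar convention for time to progression, but the plan does not state it, and it does not turn the median into a description of all registered patients. The origin is a minor matter.

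**Conclusion.** The concern holds as a defect of definition and recording. The plan gives no rule for death without progression or for absent scans. If deaths are censored, the median can be reached with documented progression in 20% to 40% of registered patients, for 60% down to 20% dead before the first scan. Those figures assume complete scanning of survivors, no earlier scan and all events at the first scan. They show a gap between estimands and do not measure bias, because progression in patients who die unscanned is unknown.

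Followed as written, 11.6.1.1 leaves 25% to 67% of boosted lesions unmeasured in patients with four to nine (at most 62.5% under the Schema's limit). The region mismatch can misclassify recurrences in the 5 mm shell, by an unknown amount. The absence of local control from 13.1.2 and 13.3 is a plain omission. These are descriptive secondary results, so the plan should be corrected, but the primary test of delayed recall is unaffected.

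**What to change.** 1. In 13.3.2.3, state the event, the censoring rules and one time origin. Report the Aalen-Johansen cumulative incidence of scan-detected progression with death as a competing event. Describe the Cox models as cause-specific, and report how many patients had no follow-up MRI. If death is meant to be an event, name the endpoint progression-free survival.
2. Reconcile 11.6.1 with Appendix II so that every boosted lesion is measured on the existing nine rows and can count as a local failure, and define which lesions are tracked. Reconcile the Schema with 3.2.1 on the lesion limit.
3. Reword the two form items to ask whether a new lesion is within or outside the hippocampal avoidance region (hippocampus plus 5 mm).
4. Add local control to 13.1.2 and 13.3 as cumulative incidence, per patient by region and per boosted lesion, with death competing. Allow for clustering of lesions within patients, for example by resampling patients or with a patient-level robust variance.

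The cost is SAP wording, a form edit and measurement of more lesions on MRIs already obtained. Stored MRIs of the 32 pilot patients may need re-reading if only one to three lesions were recorded or the region item was taken literally. No new scan is needed, but 11.6 (every 3 months to 2 years) and Appendix I (nothing between 12 and 24 months) should be reconciled so that the scan schedule behind the estimate is clear.
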